12.2 Central Coordination

A Project Manager will coordinate the day-to-day management of the study. A computerized study database will be created by an appointed Data Manager and managed at the data management centre at the CIHR Canadian HIV Trials Network. Electronic CRFs will be used.

12.3 Communication

Regular investigator meetings will be planned by teleconference to keep study personnel informed of study progress, and to encourage ongoing recruitment. Brief updates will be provided to meet enrolment targets. The information on criteria for study participation will be posted on the websites of the different clinical centres.

13.0 DETAILS OF STATISTICAL ANALYSIS

13.1. Sample size considerations

128 women, 64 per group, are required to detect a difference of 1% in the annual change in spine BMD at 48 weeks between those randomized to immediate switch to TAF/FTC vs those randomized to delayed switch to TAF/FTC with a two sample t test, assuming a standard deviation (SD) of 2%, 80% power and a significance level of .05. The difference of 1% is believed to be a clinically important difference to detect. The expected rate of loss in BMD in peri- and post-menopausal women is 1-3% per year.

The SD in the % change in BMD was estimated from several studies of BMD in HIV+ individuals. Yin et al ⁴⁹ compared longitudinal changes in BMD in pre and post-menopausal HIV+ and uninfected women in two separate cohorts. In the premenopausal period annual % decrease in BMD was not different in HIV+ and HIV- at the lumbar spine (LS) (-0.8 +/-2.1% vs 0.4 +/-1.9%, p=.20) and remained similar after adjusting for traditional risk factors. In the postmenopausal period annualized rates of bone loss adjusted for baseline BMD were higher in HIV+ women by 2.4 fold at the LS (-1.2 vs -0.5 %, p<.00009). In a randomized study, where participants were 90% men, mean age 40, switching from TDF to TAF containing regimens

showed a statistically significant increase in BMD (median(IQR) + 1.79 % (-.22%, 3.38%)vs 0.28% loss(-2.25,1.5%), p<.001).²¹ Another study (85 % men, median age 49) showed a mean increase in BMD of 1.5% at 48 weeks with a switch from TDF to TAF compared to a .2% loss in those continuing TDF. ²⁹A third study in persons with impaired renal function switching from a TDF to TAF containing regimen resulted in a mean increase in BMD of 2.29% at the spine and 1.47% increase at the hip.²²

13.2 Primary analysis:

Generalized linear mixed models (GLMM) will be used to estimate the effect of immediate vs delayed switch from TDF/FTC to TAF/FTC on the percent change in BMD at the spine at 48 weeks.

In the GLMM model of percent change in BMD at the spine, each patient shall contribute two data points: the percent change in BMD at the spine at 48 weeks and the percent change in BMD at the spine at 96 weeks. A variogram will be used to determine the amount of error due to random effects and serial correlation. If random effects are the source of a significant amount of variation, terms for random intercept and random time shall be included in the model. If serial correlation is determined to be the main source of error, a single parameter will be required to model the correlation between the week 48 and week 96 values from a single patient, since there will be only two BMD values per patient after enrolment.

The model shall contain four covariates: (1) treatment arm, (2) a binary indicator for whether or not the data point corresponds to week 96, (3) the interaction between the treatment arm and the 96 week indicator and (4) a binary for country (Canada vs Italy). If sufficient woman are receiving hormone replacement therapy, an additional binary covariate may be included to capture whether or not the woman was receiving hormone replacement therapy at randomization.

The GLMM model can be expressed as follows:

$$Y = \beta_0 + \beta_1 \text{ treatment} + \beta_2 \text{ week 96} + \beta_3 \text{ treatment* week 96} \quad (1)$$

where Y is the percent change in BMD at the spine.

The hypothesis test for the primary analysis is $H_0: \beta_1 = 0$, which corresponds to the primary hypothesis of the effect of switching from TDF to TAF on percent change in BMD at the spine at 48 weeks.

13.3 Secondary analyses:

The secondary endpoints of greatest importance are: the percent change in BMD at the hip at week 48, the percent change in BMD at the hip at week 96, and the percentage change at the spine at week 96. GLMM will be used to estimate the effect of immediate switch to TAF/FTC on these outcomes

The hypothesis test for the secondary analysis is $H_0: \beta_3 = 0$ in model (1) above, which corresponds to the secondary hypothesis of the effect of switching from TDF to TAF on percent change in BMD at the spine at 96 weeks.

A similar model will be fit for the outcome of percent change in the spine. In that model, the hypothesis tests of $H_0: \beta_1 = 0$ and $H_0: \beta_3 = 0$ will both be of interest, corresponding to the secondary hypotheses of the effects of switching from TDF to TAF on percent change in BMD at the hip at 48 and 96 weeks, respectively.

Interactions terms will be used to determine if the effect of switching from TDF/FTC to TAF/FTC on 48 week endpoints varies between peri and post-menopausal women or according to whether a protease inhibitor is used as the third ARV.

Other secondary endpoints such as the change in TBS at the hip, the proportions of patients with viral load < 50 copies/mL and the mean eGFR at 48 and 96 weeks will be summarized over time by treatment group to provide preliminary information but will not be compared formally to avoid type 1 errors due to multiple comparisons.

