8.4 Final Study Visit (Week 96 +/- 14 days)

The duration of the study is 2 years per participant. Participants will be recruited during the first year of the study and will be followed for 96 weeks. The final visit will be the participant's last follow-up visit and the following assessments will take place:

- Complete Physical Exam
- Vital Signs
- Hematology and biochemistry: CBC with differential and liver profile (AST, ALT), serum creatinine, calcium, phosphate, Urinalysis, GFR, Urine albumin/creatinine, urine protein/creatinine, lipids- cholesterol, LDL, HDL, TG, glucose. CD4/CD8
- Urine pregnancy test and FSH (if premenopausal)
- HIV Viral Load
- Research Blood Sample
- Questionnaires- quality of life, adherence, falls, balance
- Frax Score determined by country specific FRAX calculator
- Framingham Cardiovascular Risk Score
- Medication review: ART and Other Concomitant Medications
- Imaging as per study site: DXA, TBS, HRpQCT
- Geriatric assessment, with questionnaires (frailty, quality of life, balance, falls), dynamometer, performance walking test.

To collect any information on potential adverse event reaction, patients will be called 4 weeks after their last visit at 96 weeks +/- 7 days.

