8.5 Early Termination

If a participant withdraws from the study early, documentation for reason of early termination is required. Investigations will be completed as per final visit.

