8.7 Schedule of Procedures

Study Weeks		W0	W4	W12	W24	W36	W48	W52	W60	W72	W84	W96/End of Study	W100
Study Visits	Screening (-30 days)	Baseline (screening + 30 days)											
Visit Duration	1-2 hours	2 hours	1 hour	1 hour	1 hour	1 hour	1-2 hours	1 hour	1 hour	1 hour	1 hour	1-2 hours	Phone call
Informed Consent Form	X												
Assign Subject ID number	X												
Randomization		X											
Demographics	X												
FRAX and Framingham Score	X						X					X	
Medical History	X												
Physical Exam ¹ Signs/ Symptoms	X (complete)	X	X	X	X	X	X (complete)	X	X	X	X	X (complete)	
Vital Signs including height, weight and determination of BMI	X	X	X	X	X	X	X	X	X	X	X	X	
Pregnancy test (if premenopausal), FSH	X ²	X	X	X	X	X	X ²	X	X	X	X	X ²	
HIV viral load ³	X	X ³	X ³	X	X	X	X ³	X ³	X	X	X	X ³	
CD4/CD8 count ³		X ³		X	X	X	X ³	X	X	X	X	X ³	
Hematology and biochemistry: CBC with differential and liver profile (AST, ALT, serum creatinine, calcium, phosphate, Urinalysis, GFR, Urine albumin/creatinine) ³	*X	X ³	X	X	X	X	X ³	X	X	X	X	X ³	
HBsAg, anti-HBcAb, HBsAb, HCV antibody ⁴	X ⁴												

Study Weeks		W0	W4	W12	W24	W36	W48	W52	W60	W72	W84	W96/End of Study	W100
Fasting glucose/cholesterol ³		X ³					X ³					X ³	
Research blood sample		X					X					X	
Study Drug dispensation		X		X	X	X	X	X	X	X	X	X	
Study Drug Accountability (pill counts)			X	X	X	X	X		X	X	X	X	
Questionnaires/assessments (calcium & vitamin D ⁵ , quality of life, adherence, frailty, falls, balance)	X ⁵	X					X					X	
Concomitant Medication review	X	X	X	X	X	X	X	X	X	X	X	X	
Dexa scan ⁶	X ⁶						X					X	
Trabecular bone score determined from DXA (participating sites)		X					X					X	
HRQCT scan (participating sites)		X					X					X	
Grip strength with dynamometer		X					X					X	
Test of balance and gait- balance tests, gait speed, chair stand		X					X					X	
Capture adverse events or changes in clinical conditions/medications		X	X	X	X	X	X	X	X	X	X	X	X

¹Targeted physical exam except at Screening, Weeks 48 and 96/end of study

² Serum pregnancy and FSH for all participants at screening. Urine pregnancy at all other visits, and FSH at Weeks 48 and 96/end of study **for pre-menopausal women only**

³Screening lab results may be within 1 month of screening visit. Lab collection and results as per site Standard of Care, except at Weeks 0, 48 and 96 (end of study) where lab collection and results are required. Repeat viral load and safety assessments should be done at Weeks 4 and 52.

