13.4. Interim analysis: no interim analyses are planned

13.5 Feasibility: The number of women on TDF/FTC aged 45-55 at UHN, MLMC, Modena and Milan are 48, 114, 105 and 80 respectively, for a total of 347. We expect that 90% (n=312) will be eligible and of those, that 80% (n=250) women would agree to participate. In addition each of the additional four Canadian sites have agreed to recruit between 5-10 participants. Therefore, it should thus be feasible to recruit the required 128 women within 12 months.

13.6 Timeline: 6 months for start- up and ethics approval, 12 months for enrollment; 24 months for follow-up; 6 months for analysis/write-up

13.7. Loss to follow-up: We expect that 10% of randomized patients will drop out before 48 weeks. Primary analyses will be conducted assuming data are missing at random. Pattern mixture models and selection models will be used as sensitivity analyses to determine the range of possible treatment effects under the assumption of not missing at random.⁵⁰

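### The 128 women in section 13.1 are the number needed with week-48 data, yet 128 is also the number to recruit and 10% are expected to drop out first

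*Combined protocol and SAP*

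**What the plan says.** Section 13.1 sets the sample size: "128 women, 64 per group, are required to detect a difference of 1% in the annual change in spine BMD at 48 weeks". The stated inputs are a two-sample t test, an SD of 2%, 80% power and a significance level of .05; sidedness is not given. Of the target difference it says: "The difference of 1% is believed to be a clinically important difference to detect". Dropout is not mentioned there.

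Section 13.5 takes the same number as the recruitment goal, calling it "feasible to recruit the required 128 women within 12 months". Section 13.7 then says: "We expect that 10% of randomized patients will drop out before 48 weeks". Its response is a primary analysis under missing at random, with pattern mixture and selection models as sensitivity analyses. No section gives a number to randomise above 128.

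For the primary model, section 13.2 says "each patient shall contribute two data points: the percent change in BMD at the spine at 48 weeks", the second being the change at week 96. For women who leave early, section 8.5 says "Investigations will be completed as per final visit". The final-visit list in section 8.4 includes "Imaging as per study site: DXA, TBS, HRpQCT", and the column in the section 8.7 schedule is headed "W96/End of Study".

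**The concern.** A sample size from a t-test formula counts women who contribute an outcome. If the same count is randomised and some are expected to be lost before the outcome is measured, the stated power cannot be the power the trial expects to have. Sections 13.1, 13.5 and 13.7 put the trial in that position.

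The primary comparison is affected, at the difference the plan itself calls clinically important. A reader of a null result would take the chance of having missed a true 1% difference to be about 20%, when the plan's own dropout figure implies about 24%.

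**Working it through.** **Inputs**

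- Difference δ = 1%, SD σ = 2%, α = .05, power 80%, two-sample t test: section 13.1.
- 1:1 allocation: section 5.0.
- 128 to recruit: section 13.5.
- 10% dropout before week 48: section 13.7.
- Two-sided testing: inferred (see step 1).

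**Formula.** With n women per group contributing data, the t statistic has 2n − 2 degrees of freedom and noncentrality δ / (σ√(2/n)). Power is the probability that its absolute value exceeds the two-sided 5% critical value.

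**Step 1: reproduce the plan's figure.** At n = 64 the noncentrality is 1 / (2√(2/64)) = 2.83, with 126 degrees of freedom, and power is 80.1%. At n = 63 power is 79.5%. So 64 is the smallest whole number per group that reaches 80%, and 2 × 64 = 128. A one-sided .05 test would need only 51 per group, so the plan's figure matches a two-sided test. It has no spare women in it.

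**Step 2: apply the plan's dropout.** 128 × 0.90 = 115.2, or 57.6 per group. If none of the lost women has a usable scan:

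| Women per group with data | Power for 1% at SD 2% | Difference detectable with 80% power |
|---|---|---|
| 64 (no loss) | 80.1% | 0.998% |
| 58 | 76.1% | 1.049% |
| 57.6 | 75.8% | 1.053% |
| 57 and 58 | 75.7% | about 1.05% |
| 57 | 75.4% | 1.059% |

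**Step 3: partial recovery.** If half of the early leavers gave a usable scan (assumed, so 5% net loss), 128 × 0.95 = 121.6, or 60.8 per group, and power is 78.1%.

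**Step 4: other SDs quoted in 13.1.** The cohort of premenopausal women cited there has SD 2.1% in HIV-positive women and 1.9% in uninfected women.

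| SD | Power at 64 per group | Power at 57.6 per group |
|---|---|---|
| 1.9% | 84.0% | 80.0% |
| 2.0% | 80.1% | 75.8% |
| 2.1% | 76.2% | 71.7% |

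The 10% loss costs about 4 points at each SD. The 2.1% row comes from HIV-positive women, which is the population enrolled here.

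**Step 5: does the planned model recover the loss?** The response in 13.2 is the percent change from baseline at weeks 48 and 96. Baseline is already inside the response, so a woman with neither scan contributes no row. The missing-at-random assumption and the sensitivity models in 13.7 concern bias; they add no information about women who were not measured.

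**Step 6: number that would keep 80%, for reference.** 64 / 0.90 = 71.1, so 72 per group or 144 in all. 72 × 0.90 = 64.8 per group gives 80.6%.

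**The case against.** The strongest reply is that dropping out need not mean having no scan. Section 8.5 asks for final-visit investigations at early termination, and these include DXA. Section 8.3 allows imaging within 4 weeks of the week-48 visit, so a scan at a late exit could fall inside the window, and women who stop study drug may stay in follow-up if they agree. This stands in part: 76% is the full-loss case, and step 3 gives an intermediate one. However, the plan gives no estimate of how many scans would be recovered. The only time term in the 13.2 model is a week-96 indicator, so it is unclear how a scan at another time would enter.

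A second reply is that the primary test is a mixed model with covariates, not a bare t test. Removing about 10% of the residual variance would bring power at 57.6 per group back to 80.1%. Country is the only adjustment covariate that is certain, and the documents claim no such gain.

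A third reply is that the SD matters more. The interquartile ranges that 13.1 quotes from a randomised switch study are 3.60 and 3.75 points wide. Divided by 1.349, assuming normality, they imply SDs of about 2.7% and 2.8%. At SD 2.7%, power is about 55% without dropout and 50% with it. That is true, but it is a separate question about the SD and does not excuse the missing allowance. In the other direction, another cited study found +1.5% against −0.2%, a 1.7-point difference. At that effect and SD 2%, power stays above 99% after 10% loss. Those participants were mostly men, and the plan is powered for 1%.

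**Conclusion.** The concern holds. The arithmetic in 13.1 is correct for women with week-48 data. It does not agree with 13.5 and 13.7, which randomise that same number and expect to lose 10% of it before the primary time point. At SD 2%, 80% power is available only if nobody is lost.

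The power the plan supports is about 76% (75.4% to 76.1%) rather than 80.1%, and the detectable difference about 1.05% rather than 1%. This assumes a two-sided test, SD 2%, loss spread about evenly across the groups, no usable early-termination scans and no gain from covariates. Some recovered scans would narrow the gap, to 78.1% at an assumed 5% net loss. The loss is about 4 points, enough to need correcting but not enough to undermine the design.

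**What to change.** Restate 13.1 along these lines, after confirming that the test is two-sided:

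> 128 women will be randomised (64 per group). With 10% expected to drop out before week 48, about 115 are expected to have week-48 data. With a two-sample t test, SD 2% and two-sided α = .05, power to detect a 1% difference is then about 76%, and the difference detectable with 80% power is about 1.05%. This assumes that early-termination scans are not used in the primary model.

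In 13.2, add one sentence saying whether an early-termination DXA value enters the primary model and, if so, at which time point. If such scans are to be used, change the last sentence of the 13.1 text and its power figure to match.

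The cost is wording only: no extra enrolment and no change to the primary test, with a slightly lower stated power. If the sponsor prefers to keep 80% under the same assumptions, 144 women (72 per group) would have to be randomised, 16 more than planned. The pool in 13.5, about 250 willing women at the main sites, would not obviously prevent that.

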8.3 Follow-up Visits for Participants

These will occur at weeks 4, 12, 24, 36, 48, 52, 60, 72, 84 and 96. At weeks 4, 12, 24, 36, 52, 60, 72, and 84, the participants will have routine investigations as per the study site, and will complete targeted physical exams. **Complete** physical exams, labwork as outlined in the schedule of Assessments on pages 25 – 26, and FSH (if premenopausal) will be required at weeks 48 and 96. Adverse events will be captured at each study visit as will any changes in clinical conditions or medications. Pill counts of returned study drug except week 52 will also be captured. The accepted windows around study visits are +/- 7 days. The procedures will last about 60 minutes.

If they agree, participants will continue to be followed even if they decide to stop the study medication

At weeks 48 and 96 all participants will complete the study imaging, collection of plasma specimens for marker banking, quality of life questionnaires, FRAX score as determined by country specific FRAX calculator, Framingham cardiovascular risk score, and geriatric measures as above. The additional procedures will last

approximately 30 minutes plus imaging time. The imaging is to be scheduled within 4 weeks of these visit dates.

Drug dispensation will be done every 3 months during the regular visits at W0, 12, W24, W36, W48, W60, W72, and 84. At week 48, all participants will receive open label TAF/FTC.

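### A variogram on two values per woman has one lag and cannot choose the primary model's covariance, so the standard error behind the β1 test is not fixed in advance

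*Combined protocol and SAP*

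**What the plan says.** Section 13.2 models percent change in spine BMD with a mixed model in which "each patient shall contribute two data points", one at week 48 and one at week 96. The primary test is β1 = 0, the arm difference at week 48.

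The covariance is left to a data-driven step: "A variogram will be used to determine the amount of error due to random effects and serial correlation". Two branches follow.

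- If random effects account for enough of the variation, "terms for random intercept and random time shall be included in the model".
- If serial correlation dominates, "a single parameter will be required to model the correlation between the week 48 and week 96 values from a single patient". The plan explains this by noting that there are only two post-enrolment values.

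The section does not say how much variation is enough for either branch, whether the two variances may differ, whether the intercept–time covariance is estimated, or how the SE and degrees of freedom are obtained.

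Section 8.3 places follow-up imaging at weeks 48 and 96 only, with some latitude: "The imaging is to be scheduled within 4 weeks of these visit dates". The same section states: "At week 48, all participants will receive open label TAF/FTC".

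**The concern.** A variogram separates sources of within-person error by showing how half the mean squared difference between residuals grows with the time between them. That needs several lags, and here there is one. Baseline adds none, because percent change is zero there by definition.

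The plan therefore names a selection rule that cannot select. In an open-label trial, the covariance for the only primary test would be chosen by judgement once outcomes are available. The branches can carry different restrictions on the two variances, so the choice can change the SE, p-value and power for β1.

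Equal variances cannot be presumed. The week-96 change covers twice the time, and the delayed arm changes regimen at week 48.

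**Working it through.** **Inputs from the documents.** 64 women per arm, difference 1%, SD 2% at week 48, 80% power and α = 0.05 (Section 13.1); two values per woman (13.2); imaging within 4 weeks of the visit (8.3); 10% dropout before week 48 (13.7).

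**Assumptions.** The documents give neither the week-96 SD nor the within-woman correlation. The ratio r = SD96/SD48 is varied from 0.75 to 1.41. The correlation is 0.6, or 0.4 to 0.8 for the selection check.

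**1. The plan's own figure.** For a two-sided two-sample t test, exact noncentral-t power is 0.795 at 63 per arm and 0.801 at 64. The 64 per arm is reproduced. The corresponding SE of β1 is 2·√(2/64) = 0.354.

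**2. One lag.** With variance 4 and correlation 0.6:

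- Random intercept only: between-woman 2.4 plus residual 1.6 gives [[4, 2.4], [2.4, 4]].
- Serial correlation only: variance 4 and ρ = 0.6 gives the same matrix.
- Variogram: γ(48) = 4·(1 − 0.6) = 1.60 under both.

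**3. Does the spread of scan dates help?** With each scan within ±4 weeks, lags run from 40 to 56 weeks. Under serial correlation:

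- γ(40) = 4·(1 − 0.6^(40/48)) = 1.39
- γ(56) = 4·(1 − 0.6^(56/48)) = 1.80

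Under a random intercept γ stays at 1.60. In 8,000 simulated trials of 128 women, with parameters known (the most favourable case) and correlation 0.4 to 0.8, the true model fitted better in 57% to 60%. A coin flip gives 50%.

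**4. The random intercept and time branch, with time as the 0/1 week-96 indicator.**

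- Var48 = τ00 + σ²
- Var96 = τ00 + 2τ01 + τ11 + σ²
- Cov = τ00 + τ01

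If τ01 is free, four parameters map to three moments (Jacobian rank 3), so the components are not identifiable. The 2×2 matrix can still be fitted: 60 of 60 simulated REML fits converged without warning. No harm to β1 is claimed for that form.

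If τ01 = 0, then Var96 − Var48 = τ11 ≥ 0, so week 96 cannot be the less variable time. The fit fell back to a common variance in 100% of simulated trials at r = 0.75, 93% at r = 0.9 and 0.5% at r = 1.2. Type I error was 8.1% at 0.75, 6.2% at 0.9, and 4.9% to 5.3% at 1.0 and above.

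**5. A common variance imposed.** With complete balanced data, the fitted variance is the average of the two, so

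SE ratio = √((1 + r²)/2).

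For example, r = 1.2 gives √(2.44/2) = 1.10. Results at 64 per arm (40,000 replicates per cell, t reference; the last row is at 58 per arm, since 0.9 × 64 = 57.6):

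| r | 0.75 | 0.9 | 1.0 | 1.2 | 1.3 | 1.41 |
|---|---|---|---|---|---|---|
| SE ratio | 0.88 | 0.95 | 1.00 | 1.10 | 1.16 | 1.22 |
| Type I error | 8.3% | 6.4% | 5.0% | 3.0% | 2.3% | 1.7% |
| Power, 64 per arm | 86% | 83% | 81% | 74% | 70% | 66% |
| Power, 58 per arm | 82% | 79% | 76% | 70% | 66% | 61% |

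Unstructured covariance gives 5% type I error throughout, with power 80% at 64 per arm and 76% at 58.

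**6. The estimate.** In simulated REML fits with r from 1.0 to 1.5, with and without dropout, β1 differed between the common-variance and unstructured fits by at most about 0.05 percentage points.

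**The case against.** The strongest reply is that the proven failure is harmless in itself. If a random intercept and serial correlation are the same model at two time points, picking the wrong one leaves β1 and its SE unchanged. Nor does Section 13.2 impose a common variance: one correlation parameter is compatible with an unstructured matrix, and the random-effects branch with a free covariance reaches the same three moments. Both points stand, and they make the harm conditional. They do not rescue the step. The branches as written can also be fitted with tied or one-sided variances, and nothing in the plan rules that out.

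Smaller points also stand:

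- The plan does fix the mean model, the hypothesis and two candidate structures. What is open is the final covariance and the criterion for choosing it.
- γ(48) against the total variance (1.60 against 4) does estimate how much error is shared within a woman. It cannot attribute that share to either source.
- The reason given for unequal variances with a clear direction, the longer interval, points to r above 1, where the cost is lost power. No specific reason is offered for r below 1, where type I error is inflated.
- If the visit windows in Sections 8.3 and 8.4 (±7 and ±14 days) add to the imaging window, lags span about 37 to 59 weeks (48 ± (5 + 6)). Correct selection rises only to about 59% to 64%.
- The drop from 80% to 76% under unstructured covariance comes from a sample size not inflated for dropout, which is a separate matter.

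**Conclusion.** The concern holds. That a one-lag variogram cannot separate random effects from serial correlation is a matter of algebra, and the permitted spread of scan dates does not change it in practice. The covariance that sets the SE of the only primary test is therefore not fixed in advance.

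The effect falls on the SE, p-value and power; the estimate barely moves. Its size rests on an assumed week-96 SD and on a common variance being imposed. With equal variances nothing is lost. If week 96 is more variable, power falls to 74% at a ratio of 1.2 and 66% at 1.41. If it is less variable, type I error rises to 6.4% at 0.9 and 8.3% at 0.75. This should be corrected before the analysis: the defect is certain, the harm is conditional and the repair is small.

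**What to change.** Delete the variogram and the two branches from Section 13.2. State instead that percent change at weeks 48 and 96 is analysed with a linear mixed model for repeated measures with an unstructured 2×2 covariance (separate week-48 and week-96 variances and one correlation), fitted by REML with a named degrees-of-freedom method such as Kenward–Roger. Apply the same specification to the hip outcomes in Section 13.3.

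All three covariance parameters are identifiable. With complete data the SE of β1 stays at 0.354 whatever the week-96 variance, in line with the t-test basis of Section 13.1. The cost is one or two sentences and at most one extra variance parameter. The planned N does not change on this account.

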8.0 STUDY VISITS

8.1 Screening visit:

The screening visit is anticipated to require 1-2 hours of the participant's time.

During this visit the following will take place:

- Informed Consent
- Assign Participant ID Number
- Demographic Information
- Medical History
- Physical Exam

- Calcium and Vitamin D intake assessment
- FRAX Score determined by country specific FRAX calculator
- Framingham Cardiovascular Risk Score
- Vital Signs including height, weight and determination of BMI
- HIV Viral load (within 1 month of screening date)
- Serum Pregnancy test and FSH (if post-menopausal)
- Hepatitis B and C (only if not previously tested)
- Hematology and biochemistry: CBC with differential and liver profile (AST, ALT, serum creatinine, Urinalysis, GFR, Urine albumin/creatinine, urine protein/creatinine) (within 1 month of screening date)
- Medication Review
- Review of Eligibility Criteria
- Dexa scan will be scheduled before baseline visit. (Dexa scan should be completed prior to Randomization.).

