8.2 Baseline Visit for Participants

Day 1- Week 0 (no more than 30 days after screening visit date)

This visit must occur within 30 days of the screening visit. (**Note:** If baseline visit is within 2 weeks of screening labwork, then available screening lab results may be used and **duplicate** lab work need not be recollected). This visit is anticipated to require 2 hours of the participant's time. A baseline visit should be scheduled if the eligibility criteria met, at which the following events will take place:

- Confirmation that eligibility criteria have been met
- Confirm Dexa Scan has been completed.
- Urine Pregnancy test (if premenopausal)
- Randomization
- Targeted Physical Exam
- Vital Signs
- Framingham Cardiovascular Risk Score
- Hematology and biochemistry: CBC with differential and liver profile (AST, ALT), serum creatinine, calcium, phosphate, Urinalysis, GFR,

Urine albumin/creatinine, urine protein/creatinine, lipids- cholesterol, LDL, HDL, TG, glucose)

- CD4/CD8
- HIV Viral Load
- Research Blood Sample
- Study Drug dispensation
- Questionnaires: all questionnaires/adherence scales should be completed to include, quality of life, frailty, and falls
- Medication review
- Trabecular bone score (TBS) will be determined from the screening DXA at selected participating sites
- Participants at selected participating sites will have HRpQCT scan
- Grip strength with the dynamometer
- Tests of balance and gait - balance tests, gait speed, chair stand

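### The primary model omits baseline spine BMD, which is measured before randomization; adding it needs no new data, but the gain is unknown and may be small

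*Combined protocol and SAP*

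**What the plan says.** Section 13.2 models percent change in spine BMD at weeks 48 and 96, with two records per woman. It states: "The model shall contain four covariates: (1) treatment arm, (2) a binary indicator" for week 96, then the arm-by-week-96 interaction and country. If enough women are on hormone replacement therapy, "an additional binary covariate may be included to capture whether or not the woman was receiving hormone replacement therapy at randomization". The primary test is of b1, the arm effect at week 48. Baseline BMD is not a covariate anywhere in section 13; it enters only as the value from which the change is computed. Section 5.3 stratifies randomization by country alone.

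The baseline value will be available. Section 8.1 says "Dexa scan should be completed prior to Randomization", the baseline visit in 8.2 includes "Confirm Dexa Scan has been completed", and a footnote to the schedule in 8.7 repeats the timing.

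On missing data, 13.7 expects 10% dropout before week 48 and says "Primary analyses will be conducted assuming data are missing at random". It adds pattern-mixture and selection models as sensitivity analyses. For women who withdraw early, 8.5 says "Investigations will be completed as per final visit", and the final-visit list in 8.4 includes DXA.

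**The concern.** If baseline BMD predicts percent change, leaving it out keeps explainable variation in the residual and widens the interval for b1. Dividing by baseline does not by itself remove such an association. The plan also has little power to spare: the 128 women carry no allowance for the expected dropout.

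There is a smaller, separate point. A woman with no post-baseline scan contributes nothing to a direct likelihood fit of this model. Missing at random then requires that, for such women, missingness depends only on arm, country and possibly hormone therapy. Adding baseline BMD makes that assumption easier to accept. The point does not cover women who miss week 48 but have a week-96 scan.

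**Working it through.** **Inputs from the documents.** Difference 1 percentage point, SD 2%, 80% power, alpha 0.05, two-sample t test, 64 per group (13.1); 10% dropout before week 48 (13.7). Sidedness is not stated; two-sided reproduces the plan's number.

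**Assumed input.** r, the within-arm correlation between baseline spine BMD and percent change at week 48. The documents do not give it, so a range of 0 to 0.4 is shown.

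**1. The plan's figure.** Standardized difference = 1/2 = 0.5. The exact two-sided t test needs 63.77 per arm, so 64 per arm and 128 in total. Power at 64 per arm is 80.1%. The stated sample size is reproduced.

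**2. After dropout.** 64 × 0.9 = 57.6 per arm, 115.2 in all. Unadjusted power is 75.8%.

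**3. Adding baseline, by formula.** Residual SD = 2 × √(1 − r²). Equivalent extra evaluable women = 115.2/(1 − r²) − 115.2.

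| r | Residual variance factor | Residual SD (%) | Power | 95% CI half-width | Equivalent extra women |
|---|---|---|---|---|---|
| 0 | 1.00 | 2.000 | 75.8% | 0.738 | 0 |
| 0.1 | 0.99 | 1.990 | 76.2% | 0.735 | 1.2 |
| 0.2 | 0.96 | 1.960 | 77.5% | 0.723 | 4.8 |
| 0.3 | 0.91 | 1.908 | 79.6% | 0.704 | 11.4 |
| 0.4 | 0.84 | 1.833 | 82.7% | 0.677 | 21.9 |

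Power returns to 80% at r = 0.313.

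**4. Adding baseline, by simulation.** The formula ignores the cost of estimating the extra coefficient, including chance imbalance in the covariate. A week-48 linear model with arm and country was simulated for 58 against 57 women, 20,000 runs per r (Monte Carlo standard error about 0.3 points per power figure).

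| r | Power without baseline | Power with baseline |
|---|---|---|
| 0 | 75.8% | 75.3% |
| 0.1 | 75.2% | 75.2% |
| 0.2 | 75.0% | 76.7% |
| 0.3 | 75.2% | 78.8% |
| 0.4 | 75.0% | 81.7% |

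The mean estimate is 1.00 with and without baseline. A longer run of 60,000 per r gave net changes of −0.49, −0.15, +0.1, +0.5 and +1.3 points at r = 0, 0.07, 0.1, 0.15 and 0.2, which puts break-even near r = 0.09.

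**5. What scan error alone could supply.** Assume equal, independent error variance s² (in %²) at both scans. The change then has error variance 2s², which cannot exceed its total variance of 2² = 4, so s² ≤ 2. The covariance of measured baseline with change is −s². Hence |r| ≤ 2/(2 × CV) = 1/CV, where CV is the between-woman coefficient of variation of baseline BMD in percent. For an assumed CV of 5%, 10% or 15%, |r| is at most 0.20, 0.10 or 0.07.

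**6. Dropout bias.** Simulated with a true effect of 1.0, 10% dropout per arm and an assumed log-odds of dropout of 1 per SD of baseline:

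- Same direction in both arms: the unadjusted estimate is 1.00 at every r.
- Opposite directions in the two arms: the unadjusted estimate is 0.97, 0.93, 0.89 or 0.86 at r = 0.1, 0.2, 0.3 or 0.4. The adjusted estimate is 1.00 to 1.01.

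**The case against.** The strongest reply is that nothing here is wrong. Unadjusted percent change is a valid randomized comparison, the stratum is in the covariate list, and 128 follows from the unadjusted test the plan names. That stands, and it is why this is an optional improvement.

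The gain may also be negligible. No correlation is given, and scan error caps |r| at 0.20 even if all variation in change were error. Within that cap (|r| of 0.07 to 0.20), the simulated net effect runs from about −0.15 to +1.3 power points. The larger gains at r = 0.3 to 0.4 need some other source of association. The only hint is in 13.1, which reports bone-loss rates from a cited cohort after adjustment for baseline BMD, without a correlation. So the larger figures are illustrations. Likewise, the change is free only in data: at r = 0 it costs about half a power point.

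Three further points are fair. The 75.8% starting point comes from not inflating for dropout, which is a separate matter. The bias figures need baseline to drive dropout in opposite directions by arm, which nothing in the documents suggests; early-termination scans and the planned sensitivity analyses limit the risk further. And scans are done at local sites (7.3) with no cross-calibration described. If scanners differ in scale, percent change cancels a multiplicative difference but a pooled raw baseline does not, which would weaken the usable r. That could shrink the gain, but it would not bias the comparison.

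**Conclusion.** The point holds as an optional improvement. The primary model leaves out a baseline variable that every woman with a computable endpoint will have, measured before randomization. The payoff is uneven: about half a power point lost if baseline is unrelated to change, roughly nothing at r = 0.1, between 1 and 2 points gained at 0.2, and about 3 to 7 points at 0.3 to 0.4. These figures rest on the planned SD of 2%, a 1-point difference, 10% dropout and an assumed r. No saving in participants should be claimed. The benefit for the missing-at-random assumption is real but secondary, and no bias is expected if dropout relates to baseline in the same way in both arms.

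**What to change.** In 13.2, pre-specify continuous baseline spine BMD and its interaction with the week-96 indicator as fixed terms in the primary model, and use baseline hip BMD in the same way in the hip models. Keep country as the randomization stratum, and add it to displayed equation (1), which omits it although the text lists it. State how baseline values from different scanners will be handled.

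The cost is one or two degrees of freedom and no new data. Because 13.2 is protocol text, the change goes through ethics review at each centre under 15.2. The trial is open-label, so the wording should be settled before any outcome data are examined by arm. A covariate added later would look like model selection.
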